1.1 Primary Objective

Phase I: To determine the maximum tolerated dose (MTD) of Pregnyl® when given with standard immunosuppressive therapy in pediatric and adult patients with high-risk or refractory acute graft-versus-host disease (aGVHD).

Phase II: To determine the proportions of complete, partial, mixed, and no response among surviving patients at days 28 after initiation of protocol therapy in pediatric and adult patients with high-risk (Arm 1) or refractory (Arm 2) aGVHD.

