6.4 Patients Who Do Not Complete All Study Treatments

A patient must receive at least 3 doses of Pregnyl to be evaluable for safety/tolerability in the phase I portion of the study. If a patient receives fewer doses and discontinues study therapy for a reason unrelated to study drug toxicity, the patient will be replaced within their assigned arm, however these patients may re-consent and enroll on the study again if they are eligible at a later time.

In the phase II portion of the study, a patient must receive at least 3 doses of Pregnyl to be assessed for response in Arm 1. In Arm 2A and 2B, a patient must receive at least 6 doses to be assessed for response. If a patient does not complete the number of doses necessary for response assessment, the patient will be replaced within their assigned arm, however these patients may re-consent and enroll on the study again if they are eligible at a later time.

7 Treatment Plan

Patients may remain on their standard of care current acute GVHD therapy, including calcineurin inhibitors, sirolimus, and systemic corticosteroids at the start of study treatment, unless any of these agents are determined to unsafe due to an unforeseen complication.

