7.5 Duration of Study Therapy

Arm 1 (high-risk aGVHD): Study treatment will be for a minimum of 7 days with study therapy continuing for an additional 5 weeks if a complete or partial response is documented at the initial response evaluation. Non-responders at 7 days will be taken off study therapy and treated at the discretion of the treating physician. The treating physician may remove patients from study participation sooner if concerns regarding safety emerge prior to completing 7 days on protocol.

Arm 2A and 2B (steroid-refractory/dependent aGVHD): Study treatment will be for a minimum of 14 days with study therapy continuing for an additional 5 weeks if a complete or partial response is documented at the initial response evaluation. Non-responders at 14 days will be taken off study

therapy and treated at the discretion of the treating physician. The treating physician may remove patients from study participation sooner if concerns regarding safety emerge prior to completing 14 days on protocol.

An exception to the above is if a patient experiences an event that fits the definition of a dose limiting toxicity (Grade 2-4 thromboembolic event, Grade 3-4 ascites or Grade 3-4 ovarian hyperstimulation syndrome). Study treatment will be permanently discontinued in this situation.

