NOTE: For Arm 2B, Dose level 5, in order to avoid using vials from more than one Lot of study product, the maximum dose is either (1) the contents of a single 10,000 IU vial, or (2) a maximum dose of 10,000 IU from multiple vials. All vials used should be from the same Lot.

IMPORTANT: RECONSTITUTED SOLUTION IS STABLE FOR 60 DAYS WHEN REFRIGERATED.

PRECAUTIONS

1. General: Since androgens may cause fluid retention, hCG should be used with caution in patients with cardiac or renal disease, epilepsy, migraine, or asthma.
2. Pediatric Use: Induction of androgen secretion by hCG may induce precocious puberty in pediatric patients treated for cryptorchidism. Therapy should be discontinued if signs of precocious puberty occur.
3. Geriatric Use: Clinical studies of PREGNYL® (chorionic gonadotropin for injection, USP) and its generic equivalent did not include subjects aged 65 and over.
4. ADVERSE REACTIONS: Headache, irritability, restlessness, depression, fatigue, edema, precocious puberty, gynecomastia, pain at

the site of injection. Hypersensitivity reactions, both localized and systemic in nature, have been reported.

9 Disease Reassessment and Response Definitions

Participants will be staged according to the Minnesota grading schema below:

GUIDE FOR GVHD STAGING

ORGAN	CLINICAL STAGE	
SKIN	1 = Rash <25% BSA	
	2 = Rash 25-50% BSA	
	3 = Generalized erythroderma	
	4 = Generalized erythroderma with bullous formation or desquamation	
LOWER GI	ADULT	PEDS
	0 = <500	(<280ml/m ²)
	1 = 500-1000	(281-555ml/m ²)
	2 = 1000-1500	(556-833ml/m ²)
	3 = >1500	(>834ml/m ²)
	4 = Severe abdomen pain with or without ileus, or stool with frank blood	
Liver	1 = Bili 2.1-3.0	
	2 = Bili 3.1-6.0	
	3 = Bili 6.1-15.0	
	4 = Bili >15.1	
UPPER GI	0 = No prolonged nausea or vomiting	
	1 = Persistent nausea, vomiting or anorexia	

Overall Grade	Organ Stage			
	Skin	Liver	Lower GI	Upper GI
I	1-2	0	0	0
II	3	1	1	1
III	-	2-4	2-3	
IV	4	-	4	

Response will be based on the following definitions:

- **Complete Response (CR):** a Stage of 0 for all organs with no additional intervening therapy for their GVHD.
- **Partial Response (PR):** improvement by at least 1 stage in all involved organs without progression in others with no additional intervening therapy for their GVHD.
- **Mixed Response (MR):** improvement in one organ with deterioration in another organ manifesting symptoms of GVHD or development of symptoms of GVHD in a new organ.

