Dose	Actual probability in theory of having a DLT at each dose	Probability of Selecting the specified dose given the probabilities of having a DLT listed in the 2nd column	Estimated Number of subjects treated at each dose level during the study
125 USP hCG/875 pg EGF/m ²	0.25	0.28	6.7
250 USP hCG/1,750 pg EGF/m ²	0.30	0.29	3.1
500 USP hCG/3,500 pg EGF/m ²	0.40	0.23	5.3
1,000 USP hCG/7,000 pg EGF/m ²	0.50	0.07	2.6
2,000 USP hCG/14,000 pg EGF/m ²	0.60	0.02	0.7
3,500 USP hCG/24,500 pg EGF/m ²	0.70	0.00	0.2
5,000 USP hCG/35,000 pg EGF/m ²	0.75	0.00	0.1

Phase II extension: Studying the efficacy of hCG (Arm 1, Arm 2A and Arm 2B)

After completion of the dose finding trial for each arm, the final doses will be carried forward into a two-stage phase II extension trial to confirm safety and make a preliminary determination of the activity level for Arm 1 and Arm 2. If the phase I trial enrolls fewer than 13 patients at the MTD, we will employ Simon’s Minmax two-stage design (Simon, 1989) with the possibility to discontinue after the 1st stage if the response rate is low.

- **Stage 1:** Enroll a total of 12 patients (including all treated at the MTD in phase I). *If 5 or more of these respond, the trial will continue to stage 2.*

- **Stage 2:** Enroll an additional 14 patients. *If 14 or more out of 26 patients respond, hCG will be considered promising for further investigation.*

If phase I trial enrolls more than 12 patients at the MTD, we will adjust the futility rule above for the two stage design with the giving number of patients enrolled at the MTD.

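### Section 6.4 replaces phase II patients who fall short of the dose minimum whatever the reason, so early deaths, toxicity stops and failures can leave the day-28 response count

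*Combined protocol and SAP*

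**What the plan says.** Section 6.4 sets a minimum of 3 doses for phase II response assessment in Arm 1. For the other arms: "In Arm 2A and 2B, a patient must receive at least 6 doses to be assessed for response". Anyone below the minimum is replaced: "If a patient does not complete the number of doses necessary for response assessment, the patient will be replaced within their assigned arm". No reason is excepted, and a replaced patient may re-enrol later. The phase I rule in the same section is narrower. It applies when a patient with fewer than 3 doses "discontinues study therapy for a reason unrelated to study drug toxicity, the patient will be replaced", so a phase I patient stopped by drug toxicity is not replaced.

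Early stops are foreseen. Section 7.5 says of events that fit the DLT definition: "Study treatment will be permanently discontinued in this situation". For Arms 2A and 2B it adds: "The treating physician may remove patients from study participation sooner if concerns regarding safety emerge prior to completing 14 days on protocol". Arm 1 has the same provision for its first 7 days.

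The phase II primary objective in Section 1.1, repeated in the synopsis, is "To determine the proportions of complete, partial, mixed, and no response among surviving patients at days 28 after initiation of protocol therapy". Section 13.1 defines the primary endpoint as CR plus PR at day 28 without limiting it to survivors. Section 13.3 plans simple proportions for day 28 and names no analysis population; its survivor wording is attached to days 7, 14, 56 and 180. Section 13.1 counts in stage 1 all patients treated at the MTD in phase I.

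**The concern.** A patient who dies early, or who needs new GVHD therapy, cannot be a day-28 responder. Section 9 defines PR as "improvement by at least 1 stage in all involved organs without progression in others with no additional intervening therapy for their GVHD", and its CR definition carries the same condition on added therapy. If such a patient stops before the dose minimum, Section 6.4 substitutes another patient instead of recording a non-response. The replacement rule can thus select on outcome, and it acts on the count of 26 that decides whether hCG is called promising.

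The survivor wording in Section 1.1 and the synopsis would also remove deaths after the dose minimum, up to day 28. Sections 13.1 and 13.3 do not carry that restriction, so the passages conflict and amending Section 6.4 alone would not settle how deaths count. Phase I patients at the MTD enter stage 1 as treated patients, without the phase II minimum being applied to them, so one count of 26 can mix two denominators.

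**Working it through.** **Exposed window.** The schedules in Section 10 give Arm 1 doses on days 1, 3, 5 and 7, and Arm 2 doses on days 1, 3, 5, 7, 9, 11 and 13. Dose 3 falls on day 5 and dose 6 on day 11. Non-responders removed at the planned day 7 or day 14 assessment have had 4 or 7 doses if dosed on schedule, so they are counted.

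**The plan's own design.** Section 13.2 gives p0 = 0.40, p1 = 0.65, alpha 0.05 and power 80%. An exact two-stage search finds no design with 25 or fewer patients. At 26 it gives n1 = 12, continue with ≥6/12, succeed with ≥15/26: alpha 0.047, power 0.809. The stated sample size is reproduced. The printed limits (≥5/12, ≥14/26) are each one lower and give alpha 0.104 and power 0.907. That is a separate matter, so both sets are shown.

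**Effect of replacement.** Let f be the share of treated patients who stop below the minimum and r their day-28 response rate. If 40% is the rate in all treated patients, the rate in counted patients is q = (0.40 − f·r)/(1 − f). With r = 0 and f = 0.10, q = 0.40/0.90 = 0.444. The first k patients (phase I at the MTD) respond at 0.40 and the other 26 − k at q.

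For Arm 2B, Section 13.2 has 13 patients still to enrol, 2 of them next at level 4. If level 5 is the MTD and there is no de-escalation, k = 13 − 2 = 11. The documents give no f, so 5–20% is assumed. Probability of calling hCG promising, r = 0:

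| f | q | Minimax, k = 11 | Printed, k = 11 | Minimax, k = 0 | Printed, k = 0 |
|---|---|---|---|---|---|
| 0 | 0.400 | 0.047 | 0.104 | 0.047 | 0.104 |
| 5% | 0.421 | 0.060 | 0.128 | 0.073 | 0.149 |
| 10% | 0.444 | 0.076 | 0.157 | 0.112 | 0.213 |
| 20% | 0.500 | 0.125 | 0.240 | 0.257 | 0.410 |

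If one early stopper in five responds (r = 0.2), f = 10% and k = 11, the minimax figure is 0.060.

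For Arm 1 (k = 6 + 10 = 16) and Arm 2A (k = 3 + 16 = 19), again without de-escalation, the minimax figures at f = 10% are 0.065 and 0.059. These are indicative only, because with more than 12 patients at the MTD Section 13.1 says the futility rule will be adjusted.

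**Death-only anchor, Arm 2B.** Section 2 gives 80–100% two-year mortality in steroid-refractory disease. Take M = 0.80 and 0.95 and assume a constant hazard h = −ln(1 − M)/730.5 per day, i.e. 0.00220 and 0.00410. Over the 10 days from dose 1 to dose 6, f = 1 − exp(−10h) = 2.2% and 4.0%. With k = 11 and minimax limits the result is 0.052 and 0.057.

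**On the estimate.** With 14 responders among 26 counted patients the rate is 53.8%. If 3 early failures had been replaced, it is 14/29 = 48.3% of treated patients.

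**The case against.** A minimum-dose evaluable set is an explicit design choice in a preliminary activity study, and Section 6.4 states it openly. If 40% and 65% were meant for that set, type I error is as designed. This stands: the documents do not say which population the rates describe.

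The stops the protocol actually describes before the dose minimum are DLT-type events and physician safety concerns. No passage ends Pregnyl early for progression or added GVHD therapy, and Section 13.2 shows 0 DLTs in 21 patients (10 + 4 + 7). This also stands and makes 20% an upper scenario, although the wording of Section 6.4 would cover any such patient.

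The death-only anchor cannot be charged to Section 6.4 alone, because the survivor wording in Section 1.1 would remove the same deaths. Nor is k strictly unaffected: the 20 phase I patients per arm are evaluable patients, and Section 6.4 also replaces phase I patients below 3 doses who stop for reasons other than drug toxicity. Both limits stand.

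Safety and survival are recorded elsewhere, and Sections 1.2 and 13.3 plan a day-28 treatment-failure proportion without a dose or survivor restriction. That endpoint is undefined, and none of these enters the go/no-go rule.

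Two stronger readings are tempting. A reader might infer that the false-promising rate is inflated to a known degree, or that every toxicity stop is a hidden non-response. The documents support neither. They give no early-stop rate and no population for the 40%, and under Section 9 a patient stopped for toxicity can still be in CR or PR at day 28.

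**Conclusion.** The missing exception is certain: phase II replacement applies whatever the reason, and no other section returns these patients to the day-28 count. Relative to all treated patients, the expected bias in the response rate is upward, provided early stoppers respond less often than the rest. Its size is not known. The false-promising rates above rest on an assumed f, on 40% meaning all treated patients and on few or no responses among early stoppers; the one anchor drawn from the documents gives a small effect. If 40% means dose-evaluable patients, type I error is unchanged and the defect is only that no all-treated response rate is planned. The gap is confined to the early window and is smaller in Arm 1. Severity is minor to moderate. High confidence applies to the missing exception, not to the size of the inflation.

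**What to change.** - **Section 6.4, phase II:** do not replace patients who started treatment and fell below the dose minimum because of death, drug toxicity, GVHD progression or new GVHD therapy. Keep them in the go/no-go denominator and classify them by Section 9 at day 28. Death, added GVHD therapy or no documented CR/PR is a non-response; a patient stopped for toxicity who meets CR or PR at day 28 is a responder. Patients who stop early for unrelated reasons may still be replaced.
- **Synopsis and Section 1.1:** reconcile the survivor restriction with Sections 13.1 and 13.3.
- **Section 13.3:** report the day-28 CR plus PR rate in all patients given at least one dose at the MTD, beside the dose-evaluable rate. Treat phase I patients at the MTD on the same basis, and count each patient once, at first enrolment.
- **Section 13.2:** state the population to which 40% and 65% apply.

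The cost is rewording, one further analysis of data already collected and a somewhat lower observed response rate. If 65% was meant for dose-evaluable patients, the all-treated rate is 0.65(1 − f). At f = 5% with no early responders this is 0.6175, and power falls from 0.81 to 0.70 under the minimax limits or from 0.91 to 0.84 under the printed limits. The target or the stated power should then be restated. If 65% was meant for all treated patients, power is unchanged.

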7.1 Arm 1 – High-Risk aGVHD

Standard of care immunosuppression, plus Pregnyl® (hCG supplementation) at assigned dose subcutaneously every other day for 4 doses

If a patient has a toxicity that fits the definition of dose limiting as defined in the phase I section below, the patient will discontinue study treatment.

Continue protocol treatment through day 7. Assess response at day 7:

- **If a complete or partial response**, the patient is eligible to receive Pregnyl maintenance at the same dose twice weekly for 10 doses beginning day 9 to 12. Refer to [section 9](#) for response definitions.
- **If no response**, the patient will be taken off study treatment

Pregnyl® dose level assignment will be done by treatment arm, with Arm 1 independent of Arms 2A and 2B.

For phase I, up to 5 dose levels of Pregnyl® will be tested; however dose levels -1 and -2 will be used only if dose level 1 proves too toxic.

Dose Level	Dose
-2	125 USP hCG/875 pg EGF/m ²
-1	250 USP hCG/1,750 pg EGF/m ²
1 (start)	500 USP hCG/3,500 pg EGF/m ²
2	1,000 USP hCG/7,000 pg EGF/m ²
3	2,000 USP hCG/14,000 pg EGF/m ²

The 1st 2 patients will be enrolled in dose level 1. The next cohort of 2 patients will not begin treatment until all patients in the current cohort have reached day 21 in order to assess for dose limiting toxicity (DLT).

Dose limiting toxicity (DLT) is defined as any of the following occurring by day 21 after the 1st dose of Pregnyl® (phase I component only):

- In males and females: Grade 2-4 thromboembolic event (CTCAE v4) i.e., any thrombosis more severe than a superficial venous thrombosis develops and treatment with anticoagulation is required
- In males and females: Grade 3-4 ascites (CTCAE v4)
- Specific to females: Grade 3-4 ovarian hyperstimulation syndrome, defined as the rapid development of enlarged, cystic, painful ovaries - refer to [section 11.2](#) for CTCAE grading guidance

Each new cohort of 2 patients will be assigned by the study statistician to the most appropriate dose level based on toxicity probabilities set for this study. The MTD will be identified when the total sample size of 20 patients is reached.

For the phase II the dose of Pregnyl will be that identified as the MTD during phase I.

7.2 Arm 2A – Steroid-Dependent aGVHD

Standard of care immunosuppression, plus Pregnyl® (hCG supplementation) at assigned dose subcutaneously every other day for 7 doses.

If a patient has a toxicity that fits the definition of dose limiting as defined in the phase I section below, the patient will discontinue study treatment.

Continue protocol treatment through day 14. Assess response at day 14:

- **If a complete or partial response**, the patient is eligible to receive Pregnyl maintenance at the same dose twice weekly for 10 doses beginning day 15 to 17. Refer to [section 9](#) for response definitions.
- **If no response**, the patient will be taken off study treatment

Pregnyl® dose level assignment will be done by treatment arm, with Arm 2 independent of Arm 1.

For phase I, up to 5 dose levels of Pregnyl® will be tested; however dose levels -1 and -2 will be used only if dose level 1 proves too toxic.

Dose Level	Dose
-2	125 USP hCG/875 pg EGF/m ²
-1	250 USP hCG/1,750 pg EGF/m ²
1 (start)	500 USP hCG/3,500 pg EGF/m ²
2	1,000 USP hCG/7,000 pg EGF/m ²
3	2,000 USP hCG/14,000 pg EGF/m ²

The 1st 2 patients will be enrolled in dose level 1. The next cohort of 2 patients will not begin treatment until all patients in the current cohort has reached day 21 to assess for dose limiting toxicity (DLT).

DLT is defined as any of the following occurring by day 21 after the 1st dose of Pregnyl® (phase I component only):

- In males and females: Grade 2-4 thromboembolic event (CTCAE v4) i.e., any thrombosis more severe than a superficial venous thrombosis develops and treatment with anticoagulation is required
- In males and females: Grade 3-4 ascites (CTCAE v4)
- Specific to females: Grade 3-4 ovarian hyperstimulation syndrome, defined as the rapid development of enlarged, cystic, painful ovaries—refer to [section 11.2](#) for CTCAE grading guidance

Each new cohort of 2 patients will be assigned by the study statistician to the most appropriate dose level based on toxicity probabilities set for this study. The MTD will be identified when the total sample size of 20 patients is reached.

For the phase II the dose of Pregnyl will be that identified as the MTD during phase I.

7.3 Arm 2B – Steroid-Refractory aGVHD

Standard of care immunosuppression, plus Pregnyl® (hCG supplementation) at assigned dose subcutaneously every other day for 7 doses.

If a patient has a toxicity that fits the definition of dose limiting as defined in the phase I section below, the patient will discontinue study treatment.

Continue protocol treatment through day 14. Assess response at day 14:

- **If a complete or partial response**, the patient is eligible to receive Pregnyl maintenance at the same dose twice weekly for 10 doses beginning day 15 to 17. Refer to [section 9](#) for response definitions.
- **If no response**, the patient will be taken off study treatment

Pregnyl® dose level assignment will be done by treatment arm, with Arm 2 independent of Arm 1.

For phase I, up to 7 dose levels of Pregnyl® will be tested; however dose levels -1 and -2 will be used only if dose level 1 proves too toxic. The reason for this expansion is lack of rise in plasma EGF levels with Pregnyl therapy in patients with the most severe aGVHD in the first 6 patients in phase 1.

Dose Level	Dose
-2	125 USP hCG/875 pg EGF/m ²
-1	250 USP hCG/1,750 pg EGF/m ²
1 (start)	500 USP hCG/3,500 pg EGF/m ²
2	1,000 USP hCG/7,000 pg EGF/m ²
3	2,000 USP hCG/14,000 pg EGF/m ²
4	3,500 USP hCG/24,500 pg EGF/m ²
5*	5,000 USP hCG/35,000 pg EGF/m ²

***NOTE: To avoid using vials from more than one Lot of study product, the maximum dose is either (1) the contents of a single 10,000 IU vial, or (2) a maximum dose of 10,000 IU from multiple vials. All vials used should be from the same Lot.**

The 1st 2 patients will be enrolled in dose level 1. The next cohort of 2 patients will not begin treatment until all patients in the current cohort has reached day 21 to assess for dose limiting toxicity (DLT).

DLT is defined as any of the following occurring by day 21 after the 1st dose of Pregnyl® (phase I component only):

- In males and females: Grade 2-4 thromboembolic event (CTCAE v4) i.e., any thrombosis more severe than a superficial venous thrombosis develops and treatment with anticoagulation is required
- In males and females: Grade 3-4 ascites (CTCAE v4)
- Specific to females: Grade 3-4 ovarian hyperstimulation syndrome, defined as the rapid development of enlarged, cystic, painful ovaries—refer to [section 11.2](#) for CTCAE grading guidance

Each new cohort of 2 patients will be assigned by the study statistician to the most appropriate dose level based on toxicity probabilities set for this study. The MTD will be identified when the total sample size of 20 patients is reached.

For the phase II the dose of Pregnyl will be that identified as the MTD during phase I.

7.4 Supportive Care

Patients will receive transfusions, infection prophylaxis (including appropriate viral, fungal, bacterial prophylaxis and preemptive viral monitoring per standard of care), growth factor support, and nutritional support according to the current University of Minnesota supportive care guidelines.

